4.2. Study Periods

All patients enrolled should participate in the following study periods:

- Screening/Baseline period
- Treatment period
- Post treatment follow up period

Each study visit is described below and shown in [Table 2](#). All patients are considered “on-study” until they complete the follow-up period, withdraw consent or are lost to follow up.

Table 2: Study Periods

Visit	Screening	Baseline	Study Treatment	Post Treatment Follow-up		
	1	2	3	4	5	6
Study Days	-30 to -7	-10 to -7	Day 1 Treatment (Procedure Day)	Week 1 - Day 7 - (±2 days)	Week 6 - Day 42 (±5 days)	Week 12 – Day 84 (±7 days)
Purpose	Study eligibility		Treatment	Safety/efficacy evaluation		

4.2.1. Screening/Baseline Period

The screening period begins once the patient has signed the study Informed Consent Form (ICF). Patients will be evaluated to ensure that they meet all of the inclusion and none of the exclusion criteria ([Section 5.1](#), [Section 5.2](#)).

4.2.2. Treatment Day

The treatment period duration is one day. An enrolled and randomized patient will receive the single treatment procedure with ClariVein RES (approximately less than 30 minutes), unless the patient opts to discontinue or experiences unacceptable toxicity during the delivery of the study drug.

4.2.3. Post Treatment Follow-up (FU) Period

Patients will be followed for safety and efficacy evaluations post treatment at Week 1, Week 6 and Week 12. Details are provided in [Table 3](#) and [Section 7.6](#).

4.2.4. Definition of End of Study

The end of study will be when all patients have completed Treatment Day 1 and the Post treatment follow-up at Week 12 or have discontinued from the study

4.2.5. Study or Site Termination

The Sponsor reserves the right to discontinue the study at any time for either clinical or administrative reasons and to discontinue participation of an individual Investigator or Investigational Site for poor enrollment or protocol noncompliance.

If the Sponsor, Investigator, Medical Monitor, or regulatory agencies discover conditions during the study that indicate that the study or a site should be terminated, this action may be taken after appropriate consultation among the Sponsor, Investigator, and Medical Monitor.

Study termination and follow-up will be performed in compliance with the conditions set forth in the guidelines for GCP, *International Conference on Harmonization of Technical Requirements for Registration of Pharmaceuticals for Human Use: Selection and Disposition of Patients*.

5. ELIGIBILITY CRITERIA

The study will be conducted in adult patients with venous insufficiency associated with incompetent saphenous veins due to superficial venous reflux. The Investigator or designee must ensure that only patients who meet all the following inclusion and none of the exclusion criteria are offered treatment in the study.

5.1. Inclusion Criteria

An individual must meet **all** the following inclusion criteria to be eligible for this study:

1. Written informed consent
2. Age ≥ 18 years ≤ 80
3. Saphenous vein reflux $> 500\text{ms}$ (0.5s), as measured by duplex ultrasound with patient in the standing position
4. Incompetent saphenous vein with vein diameter ≥ 4 mm and ≤ 12 mm, as measured by duplex ultrasound with patient in the standing position
5. Incompetent saphenous vein with treatable length ≥ 10 cm, as measured by duplex ultrasound with patient in the standing position
6. One or more of the HASTI symptoms related to the target vein: heaviness, achiness, swelling, throbbing and itching.
7. Candidate for endovenous procedure for the treatment of venous insufficiency or superficial venous reflux.
8. CEAP Score: C2 (symptomatic), C3, C4, C5
9. rVCSS ≥ 3

5.2. Exclusion Criteria

An individual will be ineligible for participation in this study if **any** of the follow criteria are met:

1. CEAP Score: C1, C2 (asymptomatic), C6
2. Second incompetent saphenous vein > 4 mm diameter in either leg
3. Arterial insufficiency demonstrated by a history of peripheral arterial disease (PAD) that would preclude the wearing of compression stockings
4. Absence of a palpable pulse at posterior tibial or dorsalis pedis and an Ankle-Brachial Index (ABI) ≤ 0.6
5. Multi-segmental axial deep venous reflux in at least two contiguous venous segments (e.g., femoral and popliteal) in the ipsilateral extremity
6. Previous surgical or endovenous procedure in the treatment section of the target vein (e.g., surgical, thermal ablation, chemical ablation, etc.)

7. Any major surgery, prolonged hospitalization, or pregnancy within 12 weeks prior to Screening (Visit 1)
8. Participation in an interventional clinical study with any investigational product (drug, biologic, device etc.) within 4 weeks prior to Screening (Visit 1)
9. Unable to:
 - a. walk unassisted; and
 - b. stand as needed for duplex ultrasound measurements of vein at scheduled visits
10. Previous superficial thrombophlebitis of the target saphenous vein with scarring in the treatment section
11. Female patients of childbearing potential with a positive result from a pregnancy test at the Screening (Visit 1), Baseline (Visit 2), or at the Day of Treatment (Visit 3)
12. Known sensitivity or allergic response to:
 - a. sodium tetradecyl sulfate (STS) or any of its ingredients; and
 - b. other products if planned for use on the study patient and there is no available alternative, e.g., local anesthetic; latex stockings, or gloves
13. Known history of anaphylaxis or presence of multiple severe allergies
14. Known high risk of thrombosis, e.g., two or more risk factors including, current use of hormonal contraception, current use of hormone replacement therapy, extended periods of immobility, cancer, obesity, recent trauma
15. Known history of deep vein thrombus (DVT) or pulmonary embolism (PE), known history of acute superficial vein thrombus, known hypercoagulable condition, post thrombotic syndrome
16. Known history of drug or alcohol abuse within 2 years of Screening (Visit 1); and/or current chronic narcotic usage, including for pain (e.g., opioids)
17. Presence of tortuous target saphenous vein, which in the opinion of the Investigator will limit vascular access and/or require more than one access site to treat patient
18. Varicosities caused by known pelvic or abdominal pathology
19. Lymphedema
20. Fibromyalgia
21. Other medical conditions or comorbidities which, in the opinion of the Investigator, could interfere with study compliance, could compromise patient care, or could interfere with data interpretation, including, but not restricted to:
 - a. severe illness
 - b. edema not due to venous disease of the legs (e.g., latent cardiac insufficiency, renal insufficiency, etc.)
 - c. documented human immunodeficiency virus (HIV)
 - d. congestive heart failure, coronary artery disease, cerebral vascular disease
 - e. active infection, tuberculosis, or sepsis
 - f. active cancer or neoplasm (excluding non-melanoma skin cancer)

- g. uncontrolled systemic disease such as diabetes mellitus, toxic hyperthyroidism, blood dyscrasias, or acute respiratory (e.g., asthma), or skin diseases

22. Any patient that, in the Investigator's opinion, would be unlikely to receive clinical benefit from the study procedure

6. TREATMENT OF PATIENTS

6.1. Study Treatment

ClariVein RES is the endovenous administration of STS injection (1% and 3%) mechanically delivered as intravenous infusion via the ClariVein for the treatment of venous insufficiency associated with incompetent saphenous vein due to superficial venous reflux.

This study is limited to the treatment of one incompetent saphenous vein per treatment procedure. Refer to [Appendix C](#) VICARES Clinical Study Procedure Manual for detailed on the treatment procedure including ultrasound measurements and calculation of the STS volume required for administration.

6.2. Study Duration

This study is limited to the treatment of one incompetent saphenous vein in one leg per treatment procedure. STS (1% or 3%) will be delivered as a single dose treatment. The ClariVein RES treatment procedure will be completed on each eligible patient on the Treatment Day (noted as Day 1), unless the patient experiences unacceptable toxicity and/or treatment is discontinued at the discretion of the Investigator or the patient.

Overall duration of the study from first patient enrolled to last patient completion of Week 12 follow-up is anticipated to be approximately 6 months. Study duration for individual study patients, including follow-up visits, is anticipated to be approximately 16 weeks (Visit 1 Screening, up to 30 days prior to treatment through Week 12 post-treatment.)

6.3. Potential Drug Interactions/Allergies

No well-controlled studies of the study drug (STS Injection 1% and 3%) have been performed on patients taking anti-ovulatory agents. The Investigator must use medical judgment and evaluate any patient taking anti-ovulatory drugs prior to initiating treatment with the study drug (STS) ([Sotradecol Package Insert 2013](#)).

Heparin should not be included in the same syringe as STS solution, since the two are labeled to be incompatible. ([Sotradecol Package Insert 2013](#)).

Patient should be observed for at least 30 minutes following treatment. The Investigator must be prepared to treat any allergic reaction to substances utilized during treatment procedure, including anaphylaxis reactions.

Emergency resuscitation equipment **must be immediately available** in the event of anaphylactic reactions.

6.4. Prior and Concomitant Treatment(s)/Therapy

All prior and concomitant medications taken within 30 days prior to the Screening (Visit 1) through completion of the last planned follow-up visit at Week 12 post-treatment (Visit 6) must be recorded in the eCRF.

At every visit, patients will be asked to confirm if there has been any change in medications taken since the last visit. Changes will be recorded on the concomitant medications eCRF and

coded using the World Health Organization Drug Dictionary Enhanced (WHODDE) and further coded against Anatomical Therapeutic Chemical (ATC) classification.

All concomitant medications are to be documented and reviewed per the Study's Inclusion/Exclusion criteria ([Section 5](#)).

6.5. Prohibited Concomitant Procedures/Therapies/Medications

Any adjunctive procedures in either leg, including phlebectomy, will **not be allowed** prior to completion of the Week 12 post-treatment visit.

6.6. Patient Numbering, Treatment Assignment or Randomization

6.6.1. Subject Numbering

Each patient is identified in the study by a unique Subject Number (Subject No.), that is assigned when the patient is first enrolled for Screening.

The randomization assignment of a patient to treatment arm Group 1 or Group 2 will be performed at a 1:1 ratio.

6.6.2. Double Blind - Study Drug

The Sponsor, CRO, Investigational Site Staff, Investigators and patients will be blinded to the study drug and will use the product assigned via a validated randomization system. The study blind will be broken after the study database has been locked upon completion of the clinical study.

6.6.3. Emergency Breaking of the Study Blind

The study blind is not to be broken under ordinary circumstances. No change in standard emergency treatment is anticipated due to a difference in the strength of the study drug. However, unblinding should not necessarily be a reason for discontinuation of the study.

6.7. Preparation, Dispensing, and Storage of Clinical Supplies

Please refer to [Appendix C](#) VICARES Clinical Study Procedure Manual for information on the preparation, dispensing and storage of clinical supplies.

6.8. Study Drug and Device Accountability

The Investigational site is responsible for receipt, storage, and accountability of the Study Product, ClariVein RES (STS and ClariVein), supplied to the Investigational site specifically for use in this clinical study, in compliance with Good Clinical Practice.

7. VISIT SCHEDULE AND ASSESSMENTS

7.1. Study Visit Schedule and Assessments

A list of all study assessments is included in [Table 3](#), which indicates with an “X” if the assessment performed at that visit.

The Screening (Visit 1) evaluation should be performed \leq 30 days prior to Treatment (Visit 3). Additional screening will be performed at Baseline (Visit 2), not less than 7 days prior to Treatment (Visit 3).

Study visits, tests and/or procedures should occur on schedule per Table 3. Any exceptions will have to be approved by the sponsor.

Table 3: Visit Schedule and Assessments

Visit	Visit 1	Visit 2	Visit 3	Visit 4	Visit 5	Visit 6
	Screening Period		Treatment Period	Post-Treatment Follow-up Period		
	Screening	Baseline	Treatment	Week 1	Week 6	Week 12
Study Day(s)	-30 to -7	-10 to -7	Day 1	Day 7 (±2 days)	Day 42 (±5 days)	Day 84 (±7 days)
Informed Consent	X					
Inclusion/Exclusion criteria	X					
Medical History	X					
Diagnosis and Extent incompetent saphenous vein	X					
Demographics	X					
Physical Exam	X		X			
Pregnancy test (serum)		X				
Pregnancy test (urine)	X		X			
Height	X					
Weight	X					
Vital signs	X	X	X	X	X	X
Hematological Assessment ^a		X		X	X	X
Intravascular Coagulation Assessment ^{b, c}		X	X	X	X	X
Adverse events	X	Continuous				
Concomitant medications and Non-Drug procedures	X	Continuous				
Ultrasound	X	X	X	X	X	X
CEAP Classification	X					X
rVCSS	X					X
HASTI symptoms – 7-day assessment			X	X	X	X
European Quality of Life scale (EQ-5D-5L)		X	X	X	X	X
VEINES-QOL-SYM		X	X	X	X	X
VAS score		X	X (Procedure only)	X	X	X
ClariVein RES procedure			X			

^a Hematological Assessments include: Hemolysis, hematocrit, reticulocyte count, haptoglobins as described in [Section 8.1](#)

^b Intravascular coagulations include Plasma fibrinogen level, Plasma D-dimer level platelet count, Prothrombin time (PT), Partial thromboplastin time (PTT) as described in [Section 8.1](#).

^c Plasma D-dimer level assessments will be conducted at: Baseline (Visit 2) immediately post Treatment (Visit 3) and at Week 1 follow-up (Visit 4); then, only at subsequent follow-up visits [Week 6 (Visit 5) and Week 12 (Visit 6)] if the D-dimer level is higher than it was at Baseline.

7.2. Pre-visit Patient Instructions

When scheduling a patient for a study visit, advise the patient to be mobile for at least 2 to 3 hours prior to arriving at the Investigational Study Site; this will facilitate obtaining precise measurements of incompetent saphenous vein.

Refer to the [Appendix C](#) VICARES Clinical Study Procedure Manual for instruction on the preparation and ultrasound procedure

7.3. Screening (Visit 1)

The study IRB approved informed consent form must be signed and dated before any screening procedures are performed, except for any laboratory tests performed as part of standard of care within the study screening window.

Patients will be evaluated against study inclusion and exclusion criteria. Patients must meet all inclusion and none of the exclusion criteria at Screening to be eligible for the study. For details of assessments, refer to [Table 3](#).

At the Investigational site, prior to ultrasound assessment of the venous system, the patient will be asked to stand or walk for 10-15 minutes.

During Screening visit (Visit 1), the Investigator/Investigational Staff will:

1. Perform all Visit 1 assessments per [Table 3](#)
2. At the end of the Screening Visit, *if the patient fails to be eligible* per the Inclusion/Exclusion criteria, the patient will be considered a screen failure and the reason for failure must be documented in the screening log.

7.4. Baseline (Visit 2)

The Baseline visit will occur -10 to -7 days prior to the Day of Treatment.

At the Investigational site, prior to ultrasound assessment of the incompetent saphenous vein, the patient will be asked to stand or walk for 10-15 minutes.

During the Baseline visit (Visit 2), the Investigator/Clinical Study Staff will:

1. Perform all Visit 2 assessment per [Table 3](#).
2. Review the preliminary ultrasound mapping of the bilateral superficial venous systems and the selected incompetent saphenous vein (which was obtained during the initial Screening (Visit 1))
3. Perform unilateral ultrasound imaging studies of the incompetent saphenous vein selected for treatment with patient in the standing position to determine:
 - a. access site (e.g., lowest point of reflux, as appropriate); and
 - b. treatment section length (TSL) and treatment section diameter (TSD) measurements.
4. Review the VEINES-QOL Sym with the patient. Instruct patient to answer the HASTI Symptom questions for 7-consecutive days prior to the arrival at the Day of Treatment visit (Visit 3).

5. At the end of the Baseline Visit, *if the patient fails to be eligible* per the Inclusion/Exclusion criteria, the patient will be considered a screen failure and the reason for failure must be documented in the screening log.

7.5. Day of Treatment (Visit 3)

On the Day of Treatment prior to treatment procedure review the VEINES-QOL Sym questionnaire; confirm that the patient has completed the HASTI symptom items daily for 7 consecutive days prior to Visit 3. Perform urine pregnancy test and document result. Reconfirm the patient is eligible for treatment. If the patient fails to be eligible per the Inclusion/Exclusion criteria, the patient will be considered a screen failure and the reason for failure must be documented in the screening log.

7.5.1. Prior to Treatment

1. Perform all Visit 3 assessments per [Table 3](#)
2. Review the Baseline ultrasound images and report
3. Perform a limited ultrasound exam to; (refer to [Appendix C](#) VICARES Clinical Study Procedure Manual)
 - a. confirm the vein to be treated and the access site; and
 - b. confirm TS (treatment section length) and TSD (treatment section diameter)
4. At the end of the screening, if patient is eligible for Treatment, prepare patient for the procedure
5. Investigator should follow their institution's protocol for vascular access.

7.5.2. Treatment Procedure

Refer to [Appendix C](#) VICARES Clinical Study Procedure Manual for the study treatment procedure.

Following the treatment procedure, apply compression stocking on the treated leg.

Instruct the patient of the following:

- a. The compression stocking must be worn for 72 hours (3 days) post treatment; and
- b. After 72 hours post treatment, patient is to wear the compression stocking only during the daytime for 2 weeks.

7.6. Post Treatment Follow up Period: Week 1, Week 6 and Week 12

At the post treatment follow up visits, the assessments must be completed as detailed in [Table 3](#).

7.7. End of the Study for Patient

End of Study for a patient occurs when the patient has completed the Week 12 post-treatment follow-up visit, withdraws consent, or is lost to follow-up.

7.7.1. Discontinuation of Study Treatment/Procedure

Patients may voluntarily discontinue from the study for any reason at any time. If a patient decides to discontinue from the study, the Investigator will make every effort (e.g. telephone, e-mail, letter) to determine the primary reason for this decision and record this information in the patient's chart and on the appropriate CRF pages. A patient may be considered withdrawn if the patient states an intention to withdraw, fails to return for study visits, or becomes lost to follow-up for any other reason.

The Investigator should discontinue the study procedure for a given patient if, he/she believes that continuation would be detrimental to the patient's well-being.

Study treatment may be discontinued if any of the following occur:

- Adverse event
- Physician's decision
- Patient/guardian decision
- Protocol deviation
- Technical problems

Patients must be discontinued if any of the following occur:

- At the time, a patient discontinues from the study, a visit should be scheduled as soon as possible, or no later than within 14 days of the decision to permanently discontinue from the study.
- If the decision to withdraw the patient occurs on Day of Treatment (Visit 3) following the initiation of the treatment procedure and the patient is determined to be evaluable as defined in [Section 6.1](#), the patient should be followed up for safety and efficacy at Week 1, Week 6 and Week 12.
- If the decision to withdraw the patient occurs on Day of Treatment (Visit 3) following the initiation of the treatment procedure and the patient is determined to not be evaluable as defined in [Section 6.1](#), that patient should be followed up for safety at Week 1.

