9.2. Post Randomization and Treatment

Individuals who sign the Informed Consent and are randomized are considered enrolled patients and will be included in the Intent-To-Treat (ITT) analysis.

Possible reasons for withdrawal (discontinuation) of a patient from the study include:

Adverse Event (AE). An adverse event, which in the opinion of the Investigator, indicates that discontinuation from study would be in the best interest of the patient. Patient will be followed and treated by the Investigator until the abnormal parameter or symptom has resolved or stabilized. The reason for termination will be documented by the Investigator on the patient's source documents.

Patient withdrawal of consent (or assent). Patient may be withdrawn from the study at any time if the patient, the Investigator, or the Sponsor feels that it is not in the patient's best interest to continue. If the patient withdraws prior to completing the Week 12 Post Treatment Follow up Visit, patient is considered Lost-to-Follow up. In this event the Investigator should make at least two documented attempts to contact the patient and to have an early discontinuation visit. The reasons for patient withdrawal should be documented on the patient's source documents, if known.

Patient noncompliant with study procedures. If a patient is withdrawn prior to treatment due to lack of compliance with study procedures, the reason for withdrawal will be documented by the Investigator on the patient's source documents.

Sponsor requests early termination of study. If patient discontinuation (post randomization and treatment) is due to early termination of the study by the Sponsor, patient will be followed per the follow-up schedule to completion of the post-treatment Week 12 visit. The reason for termination will be documented by the Investigator on the patient's source documents.

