11.10. Protocol Deviations/Violations

Protocol deviations will be identified prior to database lock and will be listed by treatment group in the clinical study report. A protocol violation occurs when the patient, Investigator, or Sponsor fails to adhere to significant protocol requirements affecting the inclusion/exclusion criteria, patient safety, or primary endpoint criteria.

Protocol violations for this study include, but are not limited to, the following:

- Failure to meet inclusion/exclusion criteria
- Use of a prohibited concomitant medication
- Failure to attend two post treatment visits: of which one is Week 12

Failure to comply with Good Clinical Practice (GCP) guidelines will result in a protocol violation. Sponsor will determine if a protocol violation will result in withdrawal of a patient from the study.

When a protocol violation occurs, it will be discussed with the Investigator and a Protocol Violation Form detailing the violation will be generated. This form will be signed by a Sponsor representative and the Investigator. A copy of the form will be filed in the site's regulatory binder and in the Sponsor's files.

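### The plan does not require Week 12 outcomes from a consenting, treated patient whom the investigator or sponsor withdraws after the Day of Treatment, and its end-of-study rules disagree

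*Combined protocol and SAP*

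**What the plan says.** **Treatment.** Section 4.2.2: "The treatment period duration is one day". After Day 1 there is no study treatment left to stop.

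**When a patient's study ends.** Section 4.2 counts patients as on study "until they complete the follow-up period, withdraw consent or are lost to follow up". Section 7.7 agrees: it ends when the patient completes Week 12, "withdraws consent, or is lost to follow-up". The definitions list (End-of-Study for Patient) and Section 4.2.4 are broader and also end it on discontinuation, without limiting the reason.

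**Who can withdraw a treated patient.** Section 9.2 lists an adverse event that in the investigator's opinion "indicates that discontinuation from study would be in the best interest of the patient". Under its withdrawal-of-consent item it also lets the investigator or the sponsor withdraw a patient on best-interest grounds at any time. Section 11.10 adds: "Sponsor will determine if a protocol violation will result in withdrawal of a patient from the study".

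**What follows.** Section 7.7.1 asks for a visit as early as can be arranged, "or no later than within 14 days of the decision to permanently discontinue from the study". Follow-up to Week 12 is expressly required in two cases: evaluable patients withdrawn on the Day of Treatment (Section 7.7.1), and early termination of the study by the sponsor, where the "patient will be followed per the follow-up schedule to completion of the post-treatment Week 12 visit" (Section 9.2).

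**Missing values.** The synopsis (Data Analysis) and Sections 11.1, 11.7 and 11.8 use LOCF for efficacy, including the Week 12 HASTI average and the reflux endpoint.

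**The concern.** A patient who has had the procedure, is willing to return and is withdrawn at, say, Week 3 by someone else's decision has an obtainable Week 12 outcome. The plan does not ask for it and carries an earlier value forward instead.

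These patients are not a random subset. They are picked out by an adverse event, a best-interest judgement or a violation, so the missing values are plausibly related to outcome. If adverse events differ between 1% and 3% STS, the loss differs by arm. The comparison of the two concentrations is the only randomised comparison in the trial, and the dose-response analyses in Sections 11.7 and 11.8 rest on it.

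**Working it through.** **1. The plan's own figure.** Inputs from Section 11.6: mean change -5.44, SD 3.52, two-sided 0.05, one-sample t-test.
- n = 25: standardised mean 5.44/(3.52/√25) = 7.73; noncentral-t power is above 99.9999%.
- n = 50: 5.44/(3.52/√50) = 10.93; power by the normal approximation is 1 to machine precision.

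The stated figure of at least 99% is reproduced. With 30% of Week 12 values missing, power remains above 99.99% even for one arm (n = 18). Power is not the issue; bias is.

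**2. The rules side by side, after the Day of Treatment.**

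| Reason for leaving | Where | Are Week 6 and Week 12 assessments required afterwards? |
|---|---|---|
| Patient withdraws consent | 7.7.2 | No, by the patient's choice |
| Sponsor terminates the study early | 9.2 | Yes, to Week 12 |
| Adverse event, investigator's opinion | 9.2 | Not stated |
| Best interest, investigator or sponsor | 9.2 | Not stated |
| Violation, sponsor's decision | 11.10 | Not stated |

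In the last three rows the patient has neither refused visits nor become unreachable, so Sections 4.2 and 7.7 would keep that patient on study. The definitions list and Section 4.2.4 would not.

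**3. Can the 14-day visit stand in for Week 12?** Generally not.
- Table 3 has no column for it.
- Section 8.2.3 schedules the 7-day HASTI diary at four points, none tied to this visit.
- The reflux endpoint is defined at Week 12.
- The carried HASTI value may come from the 7 days after treatment, within the compression period of Section 7.5.2. A patient with no post-treatment HASTI value leaves the MITT population (Section 11.2.2).
- Exception: the Week 12 window opens on Day 84 - 7 = 77, so a decision from Day 77 - 14 = 63 onward could place the visit inside it.

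**4. Size, for illustration.** The documents give neither a withdrawal rate nor the error of a carried value. Assume k = 3 to 6 patients and an error e = 2 to 4 points, all in the same direction.
- Pooled mean: shift = k·e/50, from 3×2/50 = 0.12 to 6×4/50 = 0.48. The 95% half-width is t(0.975, 49)×3.52/√50 = 1.00.
- Arm contrast, all k in one arm: shift = k·e/25, from 3×2/25 = 0.24 to 6×4/25 = 0.96. The half-width is t(0.975, 48)×3.52×√(2/25) = 2.00. This takes SD 3.52 in each arm and ignores the baseline covariate.
- Reflux: one carried result is 1/25 = 4 percentage points of an arm, or 1/50 = 2 points pooled.

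A second parameterisation: 20% are withdrawn in one arm and none in the other, and the carried value shows a fraction f of the planned change. The contrast shifts by 5.44×0.20×(1 - f), which is 0.54 at f = 0.5 and 1.09 at f = 0. The difference detectable with 80% power at 25 per arm is 3.52×√(2/25)×(1.960 + 0.842) = 2.79.

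**The case against.** Several stronger readings are tempting, and the documents do not support them.

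- *Section 7.7.1 itself lets the investigator end follow-up for an adverse event or deviation.* Its list of those reasons concerns stopping the study treatment. The authority to end participation comes from Sections 9.2 and 11.10.
- *The 14-day visit cancels Visits 4 to 6.* No section says so, and Section 7.6 requires the follow-up assessments in general terms. The supportable statement is that nothing expressly requires them once a patient has been discontinued.
- *Safety follow-up stops.* Sections 9.2 and 10.13 follow adverse events to resolution or stability, and Section 10.3 allows extra examinations. Only the scheduled assessments lose their express requirement.
- *Noncompliance is another exit after treatment.* Section 9.2 words it for withdrawal before treatment.
- *One clear on-study rule is breached elsewhere.* The plan holds two end-of-study rules. Section 9.2 also labels anyone who withdraws before Week 12 as lost to follow-up, which does not fit a patient still in contact.

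It is also fair to say that the magnitudes are assumed and that a 4-point error is 74% of the planned change (4/5.44). One listed violation, missing two visits including Week 12, leaves no Week 12 value to save. Section 11.8 plans observed-cases analyses for continuous endpoints, but these cannot recover values never collected.

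These points limit the scope and size of the concern. They do not supply a requirement to collect Week 12 outcomes from a consenting patient withdrawn after the Day of Treatment.

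**Conclusion.** The concern holds for consenting patients withdrawn after the Day of Treatment by an investigator or sponsor decision. The end-of-study rules conflict, the remaining assessments are not required, and LOCF fills Week 12 although already scheduled visits could supply it.

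A reader might infer that the primary result is at risk. It is not: the pooled shift of 0.12 to 0.48 is 2% to 9% of the planned 5.44-point change, and power is unaffected in practice. The exposure is in the 1% versus 3% comparison. There the illustrative shift of 0.24 to 0.96 is at most about half of the 2.00 half-width, and reaches that only if all six patients are in one arm with errors in the same direction. The problem is worth correcting before the data are collected, because an outcome not collected cannot be recovered at analysis; it is not fatal to the trial.

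**What to change.** Reconcile the definitions list and Sections 4.2, 4.2.4, 7.7, 7.7.1, 9.2 and 11.10 as follows.

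1. Once STS has been given, an investigator or sponsor decision for an adverse event, best interest or a violation is recorded with its date and reason, but does not by itself end outcome collection.
2. Patients who still consent are asked to attend the remaining Visits 4 to 6 with the Table 3 assessments, including the HASTI diary and ultrasound.
3. Observed Week 12 values from these patients are used in place of LOCF. State openly that outcomes are analysed regardless of the recorded decision.
4. Record and flag any adjunctive procedure before Week 12, which Section 6.5 prohibits, so that affected values can be identified.
5. Keep the 14-day visit for patients who decline further scheduled visits but have not withdrawn consent under Section 7.7.2.
6. Separate investigator and sponsor decisions from the withdrawal-of-consent item in Section 9.2, and do not label a patient still in contact as lost to follow-up.

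Clinical care decisions stay with the investigator. The cost is a wording amendment and some extra contact effort for a few patients; the visits are already in the schedule.
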